 - Stratified block randomization will be used to ensure that the number of participants is equally distributed among the study groups and stratified by surgery level (major, minor). The allocation sequence will be generated with block size of 4 using computer software. Randomization will be implemented with the REDCap Randomization module. Randomization schedule can only be accessed by a research personnel not directly involved in patient care. The patient's 6-week postoperative visit will be scheduled according to her assigned group.
- Study instruments:
 - Study instruments will be administered at the preoperative visit and the 6-week postoperative visit. The questionnaires for this study include the Patient Preparedness Questionnaire (PPQ), the Patient Satisfaction Questionnaire-18 (PSQ-18), and modified patient and provider preference questionnaires entitled, Patient Postoperative Visit Questionnaire and Provider Postoperative Visit Preference Questionnaire.
 - The PPQ will be administered during the preoperative visit to assess patient knowledge and preparedness for surgery, which has been demonstrated in other studies to impact postoperative satisfaction, perceived complications, and drug utilization.¹⁰⁻¹¹ The PPQ is a 11-item questionnaire scored on a six-point Likert scale and has responses ranging from 1 (strongly agree) to 6 (strongly disagree).⁹ The questionnaire for this study will utilize the same six-point scale with a reversed scoring system, ranging from 1 (strongly disagree) to 6 (strongly agree). Although there are currently no validated measures to assess surgical preparedness in urogynecology, the PPQ has been used in several studies assessing surgical preparedness in women undergoing pelvic organ prolapse and/or stress urinary incontinence.^{8,12} These studies utilized the same cutoff score for question 11 (i.e., an answer of "strongly agree" to the question "overall, I feel prepared for my upcoming surgery") to define meeting criteria for preoperative preparedness.
 - The PSQ-18 will be administered after the 6-week postoperative virtual or in-office visit to assess patient satisfaction with their postoperative visit. The PSQ-18 is a

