- All questionnaires can be completed either with paper forms or electronically through Research Electronic Data Capture (REDCap), depending on patient/provider preference. Study participants will be reminded within 48 to 72 hours after their visit regarding completion of their questionnaires by telephone call using a standardized phone script or by text or email message after their preoperative visit and their 6-week postoperative visit. Reminders for survey completion will be sent up to two times.

- Preoperative Visit
 - The preoperative visit will take place per our standard protocol, which includes a thorough discussion of the surgical purpose, alternatives, benefits, risks/complications, and postoperative expectations. Following informed consent, study-related procedures during the preoperative visit include study randomization, and scheduling of postoperative visits per study protocol. The PPQ will also be administered during this visit.
- Postoperative Visit (6 weeks)
 - Prior to the 6-week postoperative visit, a study investigator will initiate a reminder to the participant by phone, email or text to remind her of her upcoming appointment using a standard script. A checklist of discussion points will be used to standardize counseling and evaluation during the 6-week postoperative visit. Both office and virtual visits will be conducted in the same manner: The provider

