 - Marital status
 - Distance from home to clinic (miles)
 - Vaginal parity
 - Menopausal state
 - Current tobacco use (Y/N)
 - BMI (kg/m²)
 - Comorbid conditions (MI, CHF, peripheral vascular disease, cerebrovascular disease, dementia, chronic pulmonary disease, connective tissue disease, ulcer disease, mild liver disease, diabetes, diabetes with end organ damage, hemiplegia, moderate or severe renal disease, any tumor without metastasis, leukemia, lymphoma, moderate or severe liver disease, metastatic solid tumor, AIDS)
 - Charlson Comorbidity Index (CCI) score
 - *Calculation for CCI: diabetes with complications, hemiplegia/paraplegia, renal disease, and malignancies, age 60-69 are assigned a score of 2; age 70-79 moderate/severe liver disease is assigned a score of 3; metastatic solid tumour and AIDS/HIV are assigned a score of 6; the remaining comorbidities are assigned a score of 1*
 - Prior prolapse surgery (Y/N; if Y, specify)
 - Prior anti-incontinence surgery (Y/N; if Y, specify)
 - Preoperative prolapse overall stage based on POP-Q exam (0, I, II, III, IV)
 - Preoperative POP-Q points (Aa, Ba, C, GH, PB, TVL, Ap, Bp, D)
 - Preference for text or email reminder communication
 - Preferred mobile phone number or email address
- B) Perioperative data will include the following:
 - Date of surgery (MM/DD/YYYY)
 - Location of OR facility
 - Surgery level (Minor, Major)
 - Surgery type
 - Concomitant procedures
 - Operative time (minutes)
 - Estimated blood loss (ml)
 - Intraoperative complications (bladder injury, ureteral kinking, bowel injury, vascular injury, EBL ≥300 ml, transfusion, conversion to open procedure, other-specify)
 - Hospital length of stay (no. of hours if <24 hours; no. of days if >24 hours)
 - If patient was admitted, was the admission planned (Y/N)

- If N, specify reason for postoperative admission
- Voiding trial results (Pass/Fail)
 - If Fail, select outcome: foley catheter reinserted, patient taught intermittent self-catheterization
- Postoperative prescriptions at discharge (name, dosing, quantity)

○ C) Six-week postoperative data will include the following:

- Date of postoperative visit (MM/DD/YYYY)
- Number of days postop at 6-week visit
- Route of postoperative visit (in-office, virtual)
 - If virtual, was an in-office visit recommended for further evaluation (Y/N); reason for office evaluation (specify)

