- Patient satisfaction (PSQ-18) total scores, as well scores in each of the 7 PSQ-18 domains, will be treated as continuous data and checked for normality. Healthcare utilization will be analyzed individually (number of phone calls, number of outpatient visits, number of emergency department or urgent care visits, number of hospital readmissions), as well as a composite of all encounter types. Adverse events will be analyzed independently but also as a composite utilizing the Clavien-Dindo Grading System for surgical complications. Attitudes toward office/virtual visits will be analyzed by comparing proportions of patients and providers who prefer a virtual visit, prefer an office visit, or have no preference.
- All analyses will be conducted using an intention-to-treat principle. Baseline demographic and clinical characteristics will be summarized using descriptive statistics. Normally-distributed continuous measures will be summarized using mean and standard deviation (SD), whereas those showing departure from normality will be summarized using median and interquartile range (IQR). Categorical measures will be summarized using number of participants and percentage. The primary end-point analysis will be designed to test whether patient satisfaction with a virtual postoperative visit is noninferior to an in-person postoperative visit, as determined by the total PSQ-18 at the scheduled postoperative visit. Noninferiority would be shown if the lower limit of the two-sided 95% confidence interval for the between-group mean difference in the primary endpoint (i.e., the difference between the mean PSQ-18 total score in the virtual group minus the mean PSQ-18 total score in the in-office group) is more than -5 points. Similar analyses will be performed for each secondary outcome. The noninferiority margin is defined as 5 points for the PSQ-18 total score and 0.5 points for the PSQ-18 domain scores, 10% absolute for composite healthcare resource utilization, and 25% absolute for composite adverse events. Planned exploratory subgroup analyses of patient satisfaction, healthcare resource utilization and adverse events based on surgery level will be additionally performed.
- All statistical analyses will be performed using JMP Pro version 17.0 software (SAS Institute, Cary, NC).
- Data will be managed in REDCap. Statistical support will be provided by the Cleveland Clinic Quantitative Health Sciences.

E. PRIVACY AND CONFIDENTIALITY

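### Randomization is stratified by surgery level, but the primary noninferiority interval has no stratum term; adding one costs almost nothing and may narrow it slightly

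*Combined protocol and SAP*

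**What the plan says.** **Randomization** (section C, Study Procedures). Allocation is "stratified by surgery level (major, minor" (two strata), and "The allocation sequence will be generated with block size of 4 using computer software". Under Preoperative Visit, "study-related procedures during the preoperative visit include study randomization", so the stratum is assigned before the operation takes place.

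**Primary analysis** (section D, Statistical Analysis). The decision rests on the "lower limit of the two-sided 95% confidence interval for the between-group mean difference in the primary endpoint", and that difference is spelled out as "the difference between the mean PSQ-18 total score in the virtual group minus the mean PSQ-18 total score in the in-office group". The limit must lie above -5: "The noninferiority margin is defined as 5 points for the PSQ-18 total score". No test, regression model, covariate or stratum term is named here or elsewhere in the document.

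**Other uses of surgery level.** The analysis plan mentions it once: "Planned exploratory subgroup analyses of patient satisfaction, healthcare resource utilization and adverse events based on surgery level will be additionally performed". In the data collection list it appears as "Surgery level (Minor, Major" among the perioperative variables, not the preoperative ones.

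**The concern.** Stratified blocks balance the arms on surgery level. If that factor also predicts PSQ-18, the difference in arm means varies less from trial to trial than a two-sample standard error assumes, because the standard error still counts the between-stratum spread as noise. The interval is then too wide and the test conservative. If the factor does not predict PSQ-18, adjustment changes almost nothing.

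What is at stake is modest: a slightly lower chance of showing noninferiority when it is true. The verdict also depends on a single limit, so the model that produces it should be fixed in advance and should match the randomization.

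A second detail is open. Any stratum term needs a definition of surgery level. The randomization value is set at the preoperative visit, while the listed variable is perioperative. The two can differ if the operation changes.

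**Working it through.** **Inputs from the documents.** 50 evaluable per group, SD 10, margin 5, significance level 0.05, 80% power, about 5% attrition, 106 enrolled (Power Analysis and Sample Size Calculation); two-sided 95% interval with limit -5 (Statistical Analysis); two strata, blocks of 4 (Randomization).

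**Assumptions, because the documents give no figure.** True difference 0; proportion q of major surgery 0.3 to 0.7; major/minor difference D in PSQ-18 total of 0 to 5 points; total SD held at 10.

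**1. The plan's own figure.** n per group = 2 × SD² × (z_α + z_β)² / margin².

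- One-sided 0.05: 2 × 100 × (1.645 + 0.842)² / 25 = 49.5, so 50 per group, 100 in total. This reproduces.
- One-sided 0.025, which is what a two-sided 95% interval implies: 8 × (1.960 + 0.842)² = 62.8, so 63 per group. This does not.
- Attrition: 100 / 0.95 = 105.3, so 106. This reproduces.

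With the noncentral t at 50 per group, power is 0.799 at one-sided 0.05 and 0.697 under the two-sided 95% rule. That mismatch is a separate matter; 0.697 is the baseline here because it goes with the stated decision rule.

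**2. Unadjusted interval.** Half-width = t(0.975; 98) × 10 × √(2/50) = 1.98447 × 2 = 3.9689.

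**3. How much variance the stratum explains.** R² = q(1 − q)D² / 100.

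- q = 0.5, D = 0, 2, 3, 5: R² = 0, 0.0100, 0.0225, 0.0625.
- q = 0.3 or 0.7, same D: R² = 0, 0.0084, 0.0189, 0.0525.

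**4. Adjusted interval.** One more parameter leaves 97 degrees of freedom, and the residual SD is 10√(1 − R²). Half-width = 1.98472 × 10√(1 − R²) × √(2/50).

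| R² | Half-width | Power, 95% rule |
|---|---|---|
| no stratum term | 3.9689 | 0.697 |
| 0 | 3.9694 | 0.697 |
| 0.01 | 3.950 | 0.701 |
| 0.02 | 3.930 | 0.706 |
| 0.05 | 3.869 | 0.719 |
| 0.0625 | 3.843 | 0.725 |

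The cost when the stratum is irrelevant is 3.9694 − 3.9689 = 0.0005 points. The largest gain in the assumed range is 0.7245 − 0.6969 = 0.028, under 3 percentage points.

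**5. Simulation of the design.** 100 participants, half major, permuted blocks of 4 within stratum, 40,000 trials per cell, Monte Carlo standard error about 0.0008 for the error rates.

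| R² | False noninferiority at true difference -5, unadjusted / adjusted | Power at true difference 0, unadjusted / adjusted |
|---|---|---|
| 0 | 0.0244 / 0.0245 | 0.695 / 0.695 |
| 0.02 | 0.0232 / 0.0242 | 0.697 / 0.704 |
| 0.06 | 0.0216 / 0.0248 | 0.701 / 0.722 |

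A second simulation randomized 106 with 5% random dropout (20,000 trials per cell, Monte Carlo standard error about 0.0011 for the error rates). With no stratum effect and half major, the mean half-width was 3.944 unadjusted and 3.946 adjusted, and the error rates were 0.0273 and 0.0274. With D = 5 and half major, half-widths were 3.946 and 3.821, power 0.701 and 0.723, and error rates 0.0211 and 0.0236. The conclusion survives block and dropout imbalance.

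**6. Other SDs.** The plan cites SDs from 2.6 to 11.8. At SD 5, unadjusted power is already 0.999. At SD 11.8 with q = 0.5 and D = 5, power goes from 0.555 to 0.574.

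**The case against.** The strongest reply is that nothing is broken. The unadjusted difference is unbiased, its interval is valid, and it errs on the conservative side, so what is offered is an efficiency preference. The benefit rests on a link between surgery level and PSQ-18 that no part of the documents states. The instrument covers areas such as communication, cost and access, which need not depend on the size of the operation. The 5-point upper bound is an assumption as large as the margin itself; at 2 to 3 points the gain is about 0.4 to 1 percentage point. The contrast, direction, interval, margin and rule are all prespecified, and read literally the contrast is already fixed as unadjusted. Nor do the documents say that major or minor status is expected to change between randomization and surgery.

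Most of this stands. No false claim becomes more likely, and the gain may be zero. It limits the point to a minor refinement but does not remove it, because the term costs 0.0005 points when it does nothing. On the literal reading, the analysis leaves out the factor used to randomize. On the looser reading, that no model has been chosen, the analyst has a choice that should be closed in advance. Either way one sentence settles it.

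**Conclusion.** The point holds as a minor efficiency and prespecification matter. Randomization uses surgery level and the primary interval, as written, does not. At 50 per group and SD 10, a stratum term changes the half-width by between +0.0005 points (no association) and about -0.13 points (5-point major/minor difference, even split), and adds 0 to under 3 percentage points of power. These sizes rest on the assumed stratum difference and case mix. The validity of a noninferiority conclusion is not in question.

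The term would not make up the shortfall between the 80% power used for sizing and the roughly 70% under the two-sided 95% rule. In these calculations power comes back to about 80% only if surgery level shifts PSQ-18 by around 10 points (0.77 to 0.82, depending on a case mix of 50% to 80% major).

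**What to change.** Add one sentence to Statistical Analysis: the primary analysis is a linear model of PSQ-18 total on arm and surgery level as randomized (major or minor, taken from the REDCap randomization record, not from the operation performed), and noninferiority is judged by whether the lower limit of the two-sided 95% interval for the adjusted difference exceeds -5. Keep the unadjusted difference as a sensitivity analysis.

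The cost is one degree of freedom (98 to 97) and a standard model in the software already named. The stratum has to be entered in order to randomize, so no new data or workflow is needed.

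The Patient Preparedness Questionnaire should not be added as part of this change. Reminders to complete it may follow the preoperative visit, at which randomization occurs, and the documents do not quantify its relation to PSQ-18. It could be a prespecified covariate only if it is completed before allocation is revealed and if participants without it stay in the analysis.

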We hypothesize that patient satisfaction with a virtual postoperative visit will be noninferior to patient satisfaction with an in-office postoperative visit

Secondary aims:

- To compare healthcare resource utilization after the postoperative visit up to 12 weeks following urogynecologic surgery between patients receiving in-office versus virtual-video postoperative visits.

We hypothesize that the virtual group will be noninferior to the in-office group based on healthcare resource utilization after the postoperative visit up to 12 weeks following surgery.

- To compare adverse events after the postoperative visit up to 12 weeks following urogynecologic surgery between patients receiving in-office versus virtual-video six-week postoperative visits.

We hypothesize that the virtual group will be noninferior to the in-office group based on adverse events after the postoperative visit up to 12 weeks following surgery.

- To evaluate patient and provider preferences/attitudes toward in-office versus virtual-video postoperative visits

C. RESEARCH PLAN

Overall Study Design

- The study is a randomized controlled noninferiority trial evaluating patient satisfaction with in-office versus virtual-video postoperative visits at six weeks following urogynecologic surgery. We aim to assess whether the intervention of virtual postoperative visit via videoconference technology is noninferior to the standard/traditional in-office postoperative visit for our primary outcome of patient satisfaction. The recruitment period will be 15 months (January 1, 2023 to March 31, 2024). The follow-up period for each participant will be 12 weeks after surgery.

Outcome Measures

- Primary Outcome:
 - Patient satisfaction as measured by the Patient Satisfaction Questionnaire-18 at the 6-week postoperative visit
- Secondary Outcomes:
 - Healthcare resource utilization as measured by patient-initiated phone calls, unscheduled in-person/virtual office visits, emergency room or urgent care visits, and inpatient readmissions after the scheduled postoperative visit up to 12 weeks following surgery
 - Adverse events after the scheduled postoperative visit up to 12 weeks following surgery
 - Patient and provider preferences/attitudes toward virtual or office visits

Eligibility Criteria

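### Secondary noninferiority claims (two hypothesised composites and seven PSQ-18 domains) have no gate on the primary, no testing order and no exploratory label

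*Combined protocol and SAP*

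**What the plan says.** Section D, Statistical Analysis, gives one explicit decision rule: "Noninferiority would be shown if the lower limit of the two-sided 95% confidence interval for the between-group mean difference in the primary endpoint", virtual minus in-office, lies above -5 points. It then adds "Similar analyses will be performed for each secondary outcome" and sets further margins: "0.5 points for the PSQ-18 domain scores, 10% absolute for composite healthcare resource utilization, and 25% absolute for composite adverse events". The same section states that total scores, "as well scores in each of the 7 PSQ-18 domains, will be treated as continuous data".

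Section B, under the secondary aims, words two of these comparisons as noninferiority hypotheses: "We hypothesize that the virtual group will be noninferior to the in-office group based on healthcare resource utilization" and "We hypothesize that the virtual group will be noninferior to the in-office group based on adverse events after the postoperative visit". Section C, Outcome Measures, lists utilization, adverse events and preferences as the secondary outcomes. The PSQ-18 domains are not on that list; their margin appears only in section D.

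Exploratory status is given to one set of analyses only: "Planned exploratory subgroup analyses of patient satisfaction, healthcare resource utilization and adverse events based on surgery level". The documents contain no testing order, gatekeeping rule, alpha allocation or other statement on multiplicity.

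**The concern.** An analysis that only estimates a difference does not need a noninferiority margin; a margin is there to support a verdict. Nine secondary quantities have one, two of them also have a noninferiority hypothesis, and all share the primary's decision rule. Because the plan uses the exploratory label for the surgery-level subgroups and nowhere else, a reader will take the other comparisons as formal.

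Two things follow. A false positive in this trial means declaring virtual visits acceptable on some outcome when they are worse by the full margin, and each ungated test adds a chance of that. Also, nothing stops the report from claiming noninferiority on a domain or composite after total PSQ-18 has failed. The safety and utilization conclusions would rest on these tests.

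**Working it through.** **Inputs.**
- Error rate per test: one bound of a two-sided 95% CI, so one-sided 0.025 (section D, Statistical Analysis). For utilization and adverse events, where more is worse, I take the relevant bound to be the upper one; the plan says only that the analyses are similar.
- Secondary tests with a margin: 7 domains + 2 composites = 9. Individual encounter types and individual adverse events have no margin and are not counted.
- Secondary tests with a stated noninferiority hypothesis: 2 (section B).
- Correlation between tests: not given, so it is varied as an assumption.

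The plan states no error rate across the secondary tests, so there is no figure of its own to reproduce on this point.

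**Worst case.** Put every true difference exactly at its margin, so that each test gives a false claim with probability 0.025.

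*Two composites.*
- Independent: 1 - 0.975^2 = 0.0494, or 4.9%.
- Assumed correlation 0.5: 4.5%.
- Ceiling under any dependence: 2 x 0.025 = 5.0%.

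*Nine tests.*
- Independent: 1 - 0.975^9 = 0.2038, or 20.4%.
- Ceiling under any dependence: 9 x 0.025 = 22.5%.
- Common correlation r: 1 minus the integral over u of phi(u) x [Phi((1.96 - sqrt(r) u) / sqrt(1 - r))]^9, evaluated numerically.

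| Assumed r | At least one false claim among nine |
|---|---|
| 0 | 20.4% |
| 0.1 | 19.2% |
| 0.3 | 16.5% |
| 0.5 | 13.5% |
| 0.7 | 10.1% |
| 0.8 | 8.3% |
| 0.9 | 6.2% |

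If instead the seven domains correlate at 0.5 (11.5% among themselves) and the composites are independent of them and of each other: 1 - (1 - 0.1149) x 0.975^2 = 15.9%.

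**With a fixed sequence.** If total PSQ-18 is tested first, the composites follow in a set order, and formal claims stop at the first failure, the chance of any false claim among those three is at most 2.5%, with each step still using the ordinary 95% CI.

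**Would a failed primary arise in practice?** With SD 10 and 50 per group (section D, Power Analysis and Sample Size Calculation), the standard error is 10 x sqrt(2/50) = 2. If there is no true difference, the 95% CI rule succeeds with probability Phi(5/2 - 1.96) = Phi(0.54) = 70.5%, so it fails about 29.5% of the time. The planned 80% power is reproduced only at one-sided 0.05: Phi(2.5 - 1.645) = 80.4%. That mismatch is a separate matter. Here it shows only that the plan should say what happens to secondary claims when the primary fails.

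**The case against.** A reader might infer that the plan carries about a 13% false-claim rate instead of a promised 2.5%. The documents do not support that. The 13% requires an assumed common correlation near 0.5, and 2.5% is the rate per test; no level across the secondary tests is stated anywhere. The objections that follow from this have weight:

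- **Size of the family.** Nine is the widest reading. The domains are components of the primary instrument, carry no hypothesis and are missing from the list of secondary outcomes. For the two composites alone the rate stays below 5%. Those two also overlap, since readmission counts in both, so some positive correlation is likely. This stands, and it is why the two-composite figure leads. It does not explain why the domains have a margin.
- **An extreme scenario.** Every difference at its margin includes a true 25-point absolute excess in adverse events. The documents do not give domain scoring, but if each item belongs to one domain and domains are item means, a 0.5 deficit in all seven implies 18 x 0.5 = 9 points on the total. The primary would then almost certainly fail: the estimate would have to exceed -5 + 1.96 x 2 = -1.08, which is 3.96 standard errors above -9. If domains are sums, the deficit is 7 x 0.5 = 3.5 points, inside the margin. So the nine-test figures are upper-end values. The first case also shows what a gate would do: it would block the domain claims that the present text allows.
- **Common practice.** Unadjusted secondary analyses beside a single prespecified primary are common in a single-centre trial of 106 patients. That is reasonable when they are labelled as supportive; here they are not.

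A reader might also infer that the main conclusion is compromised. It is not: the primary contrast, margin and rule are single and prespecified.

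**Conclusion.** The point holds as a gap in the plan for secondary claims. As written, formal noninferiority could be claimed on either composite or any domain without the primary having succeeded. The worst-case chance of at least one false claim is 4.5% to 4.9% for the two hypothesised composites (assumed correlation 0.5, and independence), against 2.5% per test. For all nine tests with a margin it is about 6% to 20% over assumed correlations from 0.9 down to 0, and cannot exceed 22.5%.

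These figures rest on three assumptions: every true difference lies at its margin, the similar analyses use the same one-sided 2.5% rule, and the correlations are as assumed. The gap itself depends on none of the numbers. This is a cheap improvement, not a flaw in the primary analysis.

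**What to change.** In section D, Statistical Analysis, replace the sentence that extends the analysis to the secondary outcomes with a short rule:

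1. Formal secondary noninferiority claims are made only if total PSQ-18 is shown to be noninferior.
2. The two composites are then tested in an order the sponsor prespecifies (for example adverse events, then utilization; the documents do not dictate either order), each by the two-sided 95% CI, and formal claims stop at the first failure.
3. The seven domains and the individual utilization and adverse event types are reported as estimates with 95% CIs and no noninferiority verdict.

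Alternatively, label all secondary outcomes exploratory and reword the two noninferiority hypotheses in section B to match.

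Either version costs a few sentences and needs no extra participants or data. The primary test and its power do not change. What is given up under the sequence is a secondary claim whenever an earlier step fails, and a formal verdict on the domains.
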